Tumors will be measured by computed tomography (CT) or magnetic resonance (MR) at baseline and at 3, 6, 9 and 12 months after the first Therapeutic Dose. A bone scan will be performed at Screening/baseline, and if probable metastatic disease is observed additional bone scans will be performed at Months 3, 6, 9, and 12. Overall tumor response at 3, 6, 9 and 12 months per RECIST criteria will be assessed centrally by independent. blinded readers. If the study site has the capability to perform flurodeoxyglucose (FDG) scans, they may be performed to assess viable tumor tissue at baseline and 3, 6, 9, and 12 months. Tumor markers [serum chromogranin A, plasma free metanephrines and normetanephrines, 24 hour urinary vanillylmandelic acid (VMA), plasma catecholamines (dopamine, epinephrine and norepinephrine), 24 hour urinary catecholamines (dopamine, epinephrine and norepinephrine) and urinary metanephrines and normetanephrines] will be evaluated by a central laboratory at intervals described in the protocol. Renal function will be assessed through either creatinine clearance or Glomerular Filtration Rate (GFR) at baseline and at the Months 6 and 12 Efficacy Visits. Evaluation of thyroid function (T3, T4 and TSH) and clinical evaluation of possible dry mouth will be performed at the 12 month Efficacy Visit. Use and dose of antihypertensive, pain and other medication required for tumor associated signs and symptoms will be recorded on an on-going basis, including on an outpatient basis. Subjectreported Quality of Life measurements will be obtained through the EORTC QLQ-C30 v3 and the NIH Quality of Life and Symptoms Questionnaire for Pheochromocytoma and Paraganglioma. The frequency of the procedures is summarized in the Schedule of Procedures.

Safety will be assessed through analyses of treatment emergent adverse events (AEs), as well as baseline and pre- and post-infusion ECGs, physical examinations, vital signs measurements, laboratory measurements (including clinical chemistry, hematology and urinalysis), and human radiation absorbed dose estimates to target lesions and normal organs.

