Endpoints:	 Primary Endpoint: The primary endpoint for this trial is the proportion of study subjects with a reduction (including discontinuation) of all antihypertensive medication by at least 50% for at least six months or two cycles Ultratrace iobenguane I 131. The primary endpoint will be assessed at the time of study completion or discontinuation, whichever occurs first. Secondary Endpoints: Proportion of subjects with overall tumor response of CR or PR per RECIST criteria, Proportion of subjects with overall tumor response of CR, PR or MR (moderate response) per RECIST criteria Bone lesion response per the Soloway Scale Tumor marker response in 24 hr urine and other serum/plasma tumor markers associated with pheochromocytoma/paraganglioma Status of hypertension and changes in blood pressure Quality of Life per the recommended guidelines from the EORTC
	 QLQ-C30 manual Symptoms as evaluated through the NIH Quality of Life and Symptoms Questionnaire for Pheochromocytoma and Paraganglioma
	Change in use of analgesics and pain medications
	• Overall survival (OS), defined as the time from the date of enrollment to the date of death from any cause. OS time will be censored at the last date the subject is known to be alive when the confirmation is absent or unknown.
	 Safety assessed by changes in lab values, physical exams or vital signs, and the occurrence of treatment emergent adverse events Human radiation absorbed dose estimates to normal organs
Sample Size:	It is anticipated that approximately 75 subjects will be enrolled to ensure that 58 subjects receive two doses and are evaluable for safety and efficacy. The one-sided alternative hypothesis of the study is that the proportion of subjects experiencing a reduction (including discontinuation) of all antihypertensive medication by at least 50% for at least six months or two cycles is 0.25, against the null hypothesis that the proportion is 0.10. Sample size of 58 subjects in the Per Protocol Set was based on a one-sided significance level of $\alpha = 0.025$ and power of 0.90 (90%).
Statistical Methods:	Summary tables and listings of demographics and baseline characteristics for all enrolled subjects will be presented. Listings of laboratory test results collected at baseline and during the study will be generated.

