Therefore, plasma free metanephrine measurement is a more sensitive test for detecting pheochromocytoma than measurement of the parent amines or other metabolites.^{26,27,28} Increased sensitivity of metanephrine levels compared with catecholamines is due to the continuous production of O-methylated metabolites in tumors from catecholamines leaking from chromaffin stores.²⁹ Similarly, measurement of plasma methoxytyramine, the O-methylated metabolite of dopamine, provides a higher diagnostic accuracy than measurement of urinary dopamine.^{20,25}

Chromogranin A is an acidic protein that is stored and released, along with catecholamines, from chromaffin granules of normal adrenal medulla and pheochromocytoma. Results of a study of samples from subjects with no tumors, with benign or with malignant pheochromocytoma demonstrate that measurement of serum chromogranin A is useful in the diagnosis of pheochromocytoma and assists in assessing the response to therapy for those with malignant disease. A progressive rise in serum chromogranin A was observed when levels from control subjects, those with benign pheochromocytoma and subjects with malignant pheochromocytoma was assessed along with a parallel rise in plasma norepinephrine. Serum chromogranin A elevation demonstrated the most significant difference between benign and malignant tumors, and in patients with benign or malignant pheochromocytoma, serum chromogranin A correlates with the weight of the excised tumor suggesting that levels reflect the tumor burden.³⁰ Indeed, chromogranin A can be used to monitor response to treatment and/or indicate relapse of disease³¹ and correlates well with plasma metanephrines and tumor mass.^{21, 32}

Similarly, plasma metanephrine concentration is a highly sensitive and specific diagnostic marker for pheochromocytoma and metanephrines strongly correlate with tumor mass.^{20,21,23,33} Free metanephrines reflect continuous production by the tumor in contrast to the sporadic secretion of catecholamines, and repeated measurements of plasma metanephrines have been used to assess tumor recurrence.^{34,35} Overall, the measurement of plasma or urinary metanephrines is superior to urinary catecholamines (sensitivity of 99% and 97% versus 86% and 84% when used for diagnosis)³⁵ and chromogranin A and metanephrine concentrations are proportional to the tumor mass.²⁰

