11.5.10 Tumor Markers

Each subject will receive a baseline evaluation of tumor markers (serum chromogranin A, plasma free metanephrines and normetanephrines), 24 hour urinary vanillylmandelic acid (VMA), plasma catecholamines (dopamine, epinephrine and norepinephrine), 24 hour urinary catecholamines (dopamine, epinephrine and norepinephrine) and urinary metanephrines and normetanephrines, during the screening/ baseline period. Additional laboratory testing for tumor markers will include measurements every two weeks during weeks 2-24, monthly during Months 7 through 12 following the first therapeutic Ultratrace iobenguane I 131 infusion and during the

long-term follow-up through assessments provided as institutional standard of care (Section 11.5.17). All tumor markers will be evaluated by a central laboratory.

Although not a requirement, it is suggested that patients refrain from smoking or eating for at least 4 hours prior to blood draws for tumor markers to ensure reliable test measurements Subjects should sit quietly for 10-20 minutes before the phlebotomy. For dietary/medication considerations before tumor marker collection please refer to the guidelines provided in the Study Manual Binder.

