13.3.2.2.2 Tumor Marker Response Proportion

Tumor markers will be assessed as stated in the Schedule of Procedures (Appendix VII). For all tumor markers, a significant increase in test value is indicative of progression, and a significant decrease is indicative of a response.

For each individual tumor marker, response criteria are defined as follows:

Complete Response (CR)	normalized, at or below ULN
Partial Response (PR)	\geq 50% decrease in baseline value
Stable Disease (SD)	any response other than CR, PR or PD
Progressive Disease (PD)	\geq 50% increase in baseline value

To be assigned a status of PR or CR, changes in tumor measurements must be confirmed by repeat assessments that should be performed no less than 4 weeks after the criteria for response are first met.

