4.3. Trial Objectives: Secondary

The secondary objectives of this trial are as follows:

- To evaluate the safety of iobenguane I 131 in subjects with malignant pheochromocytoma/paraganglioma, including human radiation absorbed dose estimates to normal organs.
- To assess the proportion of subjects with overall tumor response of CR or PR per RECIST criteria.
- To assess the proportion of subjects with overall tumor response of CR, PR or MR (moderate response, i.e., decrease in the sum of the longest diameters of the target lesions of 15-30%, with no evidence of progressive disease [PD] in non-target lesions) per RECIST criteria.
- To assess status of bone lesions using the Soloway Scale.
- To assess tumor marker response in 24 hr urine and other serum tumor markers associated with pheochromocytoma/paraganglioma.
- To describe changes from baseline in the overall QoL through the EORTC QLQ-C30 questionnaire post-treatment.
- To describe changes from baseline in symptoms using the NIH Quality of Life and Symptoms Questionnaire for Pheochromocytoma and Paraganglioma post-treatment.
- To assess change in use of analgesics and pain medications.
- To describe Karnofsky Performance Status post-treatment.
- To assess overall survival, up to 5 years post-treatment.

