7.4.7. Tumor Markers

Tumor markers (e.g., serum chromogranin A) will be assessed as stated in the Schedule of Procedures. For each individual tumor marker, results will be categorized per the response criteria in the following table. If the tumor marker value prior to dosing is less than 1.5 times the upper limit of normal for the respective marker, it will not be included in this analysis.

Response	Criteria for Response
Complete Response (CR)*	Normalized, at or below upper limit of normal (ULN)
Partial Response (PR)*	$\geq 50\%$ decrease in baseline value but above the ULN
Stable Disease (SD)	Any response other than CR, PR or PD
Progressive Disease (PD)	$\geq 50\%$ increase in baseline value
Not Evaluable (NE)	Below 1.5 X ULN at baseline, or baseline missing

* To be assigned a status of CR or PR changes in tumor marker measurements must be confirmed by repeat assessments

For the Full Analysis Set, summary tables for confirmed tumor marker response, for each marker, will be prepared by visit window and all measurements of tumor markers will be listed. A confirmed response will require that the subsequent tumor marker assessment be identical or better compared with the previous response assessment.

Subjects will be evaluated to determine the best confirmed response for each tumor marker that is ≥ 1.5 x ULN at baseline. A listing of the best confirmed response for each tumor marker, at what time it becomes apparent, and the duration of any positive response (CR or PR) will be generated. The response is considered to be ended when the tumor marker response becomes confirmed at SD or PD.

Each subject will also be evaluated to determine if that subject is an overall tumor marker responder. An overall responder will be a subject who achieves a best confirmed response of either CR or PR at some time point, on each of the plasma and urine tumor markers that were abnormal at baseline, with the exception of urine VMA.

An additional analysis will be performed where the tumor marker response will be summarized for the dominant tumor marker for each subject. The dominant tumor marker will be identified prior to database lock by the Medical Monitor.

Analysis will determine if there is an association between achieving an overall best tumor marker response of CR or PR with achieving primary endpoint responder status based on the reduction in antihypertensive medications.

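### The SAP's overall tumor-marker responder rule names only plasma and urine markers, so read literally it omits serum chromogranin A without saying so

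*Protocol*

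**What the plan says.** The Protocol's Study Outline gives the secondary endpoint as "Tumor marker response in 24 hr urine and other serum/plasma tumor markers associated with pheochromocytoma/paraganglioma". Section 11.5.10 labels each marker by specimen and begins: "Each subject will receive a baseline evaluation of tumor markers (serum chromogranin A, plasma free metanephrines and normetanephrines". The rest of the panel is plasma catecholamines, 24-hour urinary VMA, 24-hour urinary catecholamines, and urinary metanephrines and normetanephrines. On the role of chromogranin A, Protocol section 7.4 states that "chromogranin A can be used to monitor response to treatment and/or indicate relapse of disease".

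The Protocol's response criteria in section 13.3.2.2.2 apply marker by marker: "For each individual tumor marker, response criteria are defined as follows". It defines no result that combines markers within a subject.

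The SAP's secondary objective (section 4.3) is "To assess tumor marker response in 24 hr urine and other serum tumor markers associated with pheochromocytoma/paraganglioma". SAP section 7.4.7 opens with serum chromogranin A as its example marker, tabulates confirmed response for each marker, and then adds an overall responder. Such a subject needs a confirmed CR or PR as best response, reached at any time during follow-up, and the markers that must show it are described in these words: "on each of the plasma and urine tumor markers that were abnormal at baseline, with the exception of urine VMA".

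**The concern.** The endpoint and the SAP objective both include serum markers, while the overall-responder rule lists only plasma and urine. Because the rule states its one exception, a second marker falling outside it looks like an oversight or an unexplained choice.

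The consequence is a subject-level rate that may not mean what its name suggests. A subject could be called an overall responder although one of the listed markers, raised at baseline, never responded. Two programmers could also derive different rates from the same sentence. SAP section 7.4.7 goes on to relate an overall best marker response to the primary endpoint, and to cross-tabulate a best overall confirmed marker response with RECIST response. Neither term is separately defined, so the same ambiguity may carry into those analyses.

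**Working it through.** The documents give no figure for this rule, so there is none to reproduce. The check is one of set membership, followed by what the rule does to each type of subject.

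**Step 1. Which markers does the literal rule count?** Panel from Protocol section 11.5.10; rule from SAP section 7.4.7.

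| Marker | Specimen | Counted as written? |
|---|---|---|
| Chromogranin A | serum | no; not named as an exception |
| Free metanephrines and normetanephrines | plasma | yes |
| Catecholamines | plasma | yes |
| Catecholamines | 24-hour urine | yes |
| Metanephrines and normetanephrines | urine | yes |
| VMA | 24-hour urine | no; named exception |

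**Step 2. What does the rule do to each type of subject?** I take a raised marker to be one at or above 1.5 times the upper limit of normal, the level SAP section 7.4.7 uses for evaluability. The rule itself says only abnormal, so this is an assumption. A counted marker is one marked yes above.

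| Group | Raised at baseline | As written | With serum added |
|---|---|---|---|
| A | counted marker(s), not chromogranin A | judged on counted markers | unchanged |
| B | counted marker(s) and chromogranin A | judged on counted markers only | must also respond on chromogranin A |
| C | chromogranin A but no counted marker | not specified | judged on chromogranin A |
| D | neither | not specified | not evaluable, under the fix below |

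Group B holds the subjects of concern: all counted markers reach confirmed CR or PR, chromogranin A never does, and the subject is an overall responder as written.

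**Step 3. Direction and size.** Let L be the number in group B counted as responders whose chromogranin A never reaches confirmed CR or PR. Let G be the number in group C who do reach it, and H the number in group C who do not. The effect of adding serum depends on how group C is handled at present:

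- If group C subjects are non-responders, the responder count changes by G − L, which can be positive or negative.
- If they are responders because no counted marker fails, the count changes by −(L + H), which is never positive.
- If they are left out, the count changes by G − L and the denominator grows by G + H, so the rate can move either way.

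Group D affects the denominator as well if those subjects are currently kept in it. The documents give no value for L, G or H, so neither the size nor the sign can be calculated.

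**The case against.** The strongest reply is that the wording is loose and nothing was meant to be excluded. The SAP objective names urine and serum markers only. Read as literally as the responder rule, it would drop the plasma metanephrines and plasma catecholamines, which the SAP plainly analyses. Naming VMA alone as an exception also suggests that every other marker counts. This stands as a plausible reading, and deliberate exclusion of chromogranin A is not established. It makes the sentence ambiguous, however, and the same edit resolves it.

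A reader might infer that the Protocol's marker endpoint is being reported without chromogranin A, or replaced by a more favourable one. The documents do not support that. The endpoint is defined per marker, and the SAP reports it per marker with chromogranin A included. Chromogranin A is not barred from being a subject's dominant marker (Table 14.2.3.2), and Listing 16.2.6.2.3.2 shows its percentage decrease beside RECIST response. The composite is a SAP addition, and no planned table title names its rate.

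A reader might also infer that the fix would stop subjects with chromogranin A progression from counting as responders. It would do so only in part. The rule uses the best confirmed response at some time point, so an early confirmed response followed by progression still qualifies, for chromogranin A as for any other marker.

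**Conclusion.** The point holds as a minor defect in one SAP definition. As written, the overall-responder rule does not match the marker set in the endpoint and the SAP objective. It can count a subject whose raised chromogranin A never responded, and it leaves subjects raised only on chromogranin A unclassified. The result is a descriptive secondary analysis; the primary endpoint, its success rule, the sample size and the per-marker results do not depend on it.

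It is tempting to conclude that the rule overstates the responder rate by some factor. That would need the share of subjects with raised chromogranin A and the share of them who fail on it while responding on everything else. The documents give neither. Protocol section 7.4 reports that chromogranin A correlates well with plasma metanephrines and tumor mass, which argues against assuming frequent discordance. Group C also means that overstatement is not certain even in direction. The finding rests on the definition alone and on chromogranin A being a serum marker, as both documents label it.

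**What to change.** In the overall-responder sentence of SAP section 7.4.7, add serum to the specimen types, so that the rule covers serum, plasma and urine markers, and keep the urine VMA exception. Add that a subject with no evaluable counted marker is classed as not evaluable for this result.

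If chromogranin A is left out on purpose, name it as a second exception and report the overall responder rate with and without it. In either case, state whether the association with the primary endpoint and the cross-tabulation with RECIST use this same definition. Settle the wording before database lock.

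The cost is one sentence, one extra derivation and a rate that may be less favourable. No new data are needed.

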5. TITLE OF STUDY

A Phase II Study Evaluating the Efficacy and Safety of Ultratrace Iobenguane I 131 in Patients with Malignant Relapsed/Refractory Pheochromocytoma/Paraganglioma

6. PROTOCOL AND EUDRACT NUMBER

This study is being conducted under protocol number: MIP-IB12B. The IND number is: and the EudraCT number is 2008-001148-38. The study will be completed according to the guidelines of International Conference on Harmonisation Good Clinical Practice. Compliance with this standard provides public assurance that the rights, safety, and well-being of trial subjects are protected, consistent with the principles that have their origin in the Declaration of Helsinki.

7. INTRODUCTION

7.1 Malignant Pheochromocytoma/Paraganglioma

Pheochromocytomas are rare tumors that arise from cells of the sympathetic nervous system and may secrete catecholamines. Such tumors are usually found within one or both adrenal glands (85%), but may arise in other areas of sympathetic nerve cells, and are then referred to as paragangliomas.²¹ About 15% are found to be malignant at the time, or immediately after, the primary tumor is discovered.¹⁷ Another 5% of individuals with pheochromocytomas are later found to have malignant or recurrent disease.

Common sites of metastatic disease include lung, lymph nodes, and bone. Although the effects of excessive catecholamine can be reduced by adrenergic blockade or blocking of catecholamine synthesis, these drugs do not halt tumor growth. Five-year survival has been 40%.¹ For malignant pheochromocytoma; radiation therapy has been palliative but not curative. Chemotherapy trials have failed to produce cures or significant remissions. A study of the CVD regimen (cyclophosphamide + vincristine + dacarbazine) in 14 patients with malignant pheochromocytoma reported a complete or partial response in 57% of patients (median duration, 21 months) in this very small patient study; importantly, disease progression occurred in 9 of the 14 patients and there were 6 deaths with short term follow-up.² Patients recently diagnosed with malignant pheochromocytoma have tumors that initially can be slow growing even though the survival rate is less than 50%; although some patients may experience minimal morbidity with survival for as long as 20 years.³ Rather than newly diagnosed non-metastatic malignant pheochromocytoma, this study will focus on patients with metastatic malignant pheochromocytoma or paraganglioma who have failed other therapies or are not candidates for chemotherapy or other curative therapies.

In this setting of more rapidly growing and progressive lesions, survival is often 24 months or less.

7.2 Carrier-Added Iobenguane I 131

Iobenguane is a guanethidine derivative structurally resembling norepinephrine, and is a substrate for the norepinephrine transporter (NET). It can be labeled with radioactive isotopes of iodine, suitable for both diagnostic and therapeutic applications. Carrier-added iobenguane I 131 has been used in combination with surgery and/or myeloablative chemotherapy as therapy for neuroendocrine cancers, including pheochromocytoma. The term, "carrier added", refers to the fact that a significant quantity of non-radioactive or "cold" MIBG is present in the iobenguane I 131 patient administered dose. In therapeutic doses of carrier-added iobenguane I 131 the molar ratio of nonradioactive to radioactive MIBG molecules approaches 2000:1.

Sisson et al.⁴ treated 5 malignant pheochromocytoma patients with carrier-added iobenguane I 131 at ten month intervals at a single institution in the US. Total administered activity was 484 mCi in 4 treatments over 15 months for the first patient, 373 mCi in 3 treatments over 8 months for the second patient, 410 mCi in 3 treatments over 17 months for the third patient, 270 mCi in 2 treatments over 3 months for the fourth patient, and 293 mCi in 2 treatments over 3 months for the fifth patient. The first two patients had predominantly soft tissue metastases and had responses in terms of disappearance of symptoms and a reduction in volume and function of tumors to < 50% of pretreatment values. These partial remissions lasted over 1 year to the date of publication. There was no significant toxicity reported. Tumor absorbed doses were stated to range between 13 and 120 Gy, but the dose estimation method was not elaborated.

Charbonnel et al.,⁵ in France, reported treatments with carrier-added iobenguane I 131 in 7 patients with metastatic pheochromocytomas (3 with only soft tissue metastases, 1 with only bone metastases, and 3 with both soft tissue and bone metastases). Treatment was with 100-200 mCi every 3-6 months. There was a decrease in catecholamines of greater than 50% in all 7 patients and a decrease in tumor mass of greater than 50% in all 7 patients. Toxicity included moderate pancytopenia in one patient with diffuse osseous metastasis after the second carrier-added iobenguane I 131 therapy course; this resolved within 3 months but recurred after the third treatment, requiring blood and platelet transfusion (cumulative dose 394 mCi). A mild increase in blood pressure was noted in 3 patients 2-3 days after treatment that resolved over several days.

Limone et al.⁶ and Konings et al.⁷ each reported 1 patient with clinical improvement following carrier-added iobenguane I 131 treatment. The authors suggest that treatment results could be improved if carrier-added iobenguane I 131 were given to patients with low metastatic tumor burden.

Brendel et al.⁸ in France reported 2 patients with malignant pheochromocytoma treated with carrier-added iobenguane I 131. One patient with bone and lung metastases received 2,030 mCi of carrier-added iobenguane I 131 over 10 courses at 3 month intervals; this resulted in remission in pain and asthenia, regression of > 50% in skull and lung tumors, and a decrease in VMA of 35%. The second patient received 950 mCi of carrier-added iobenguane I 131 over 5 courses at 3 month intervals. She had normalization of VMA levels and a > 50% reduction in the volume of metastatic lymph nodes. Side effects included transient leukopenia. One patient had unstable hypertension and nausea 48-72 hours after each treatment.

Troncone et al.⁹ in Italy reported treatment with carrier-added iobenguane I 131 of 4 patients with advanced pheochromocytoma. One patient with residual tumor received 300 mCi in 3 courses

at 3 month intervals and had complete regression of tumor, normalization of catecholamine levels, and no evidence of disease 20 months after start of therapy. Another patient with metastases had an 18 month remission after 670 mCi carrier-added iobenguane I 131 over 9 courses at 3 month intervals, but refused further treatment and died 6 months later. The third patient died after 15 months stabilization of the disease following 340 mCi carrier-added iobenguane I 131 over 3 courses. No change was noted in the fourth patient with massive abdominal recurrence who received only 150 mCi carrier-added iobenguane I 131 and died 2 months later. There were no adverse reactions reported.

Shapiro et al.¹⁰ investigated 28 patients at a single institution in the US. These patients had pheochromocytoma histologically-proven metastatic invasive. unresectable or pheochromocytoma, all of which were avid for tracer doses of carrier-added iobenguane I 131. Patients received 1 to 6 carrier-added iobenguane I 131 treatments, ranging from 97 to 301 mCi of administered activity; cumulative doses ranged from 111 to 916 mCi. Mild radiation sickness (nausea, vomiting and anorexia) occurred in 75.0% (21 of 28). Minor degrees of leukopenia and thrombocytopenia were observed in 10.7% (3 of 28). There were three cases of hypothyroidism but no significant hepatic, renal, adrenocortical, or autonomic nervous dysfunction. The authors found partial responses both in terms of tumor shrinkage and in terms of decreases in biochemical secretion. The tumor response (with 95% confidence interval, or CI) was 28.6% + 16.7% (8 of 28 evaluable patients). The biochemical response (95% CI) was 42.9% + 18.3% (12 of 28 evaluable patients).

Krempf et al.¹¹⁻¹² studied 15 patients with malignant pheochromocytoma at 6 centers in France. Four patients had only soft tissue metastases, 4 had only bone metastases, and 7 had both bone and soft tissue metastases. Ages ranged from 28 to 75 years. Patients were administered 740 megabequerel/mg of carrier-added iobenguane I 131 every 3 months. The number of courses ranged from 2 to 11, administered activity per course ranged from 78.4 to 250.0 mCi, and cumulative activity ranged from 300.0 to 2,322 mCi. The cumulative absorbed dose in tumors ranged from 12 to 155 Gy. One patient with widespread bone metastases developed pancytopenia after three courses (348.6 mCi); however, this resolved after treatment was discontinued. The tumor response (95% CI) was $33.3\% \pm 23.9\%$ (5 of 15 evaluable patients); duration of tumor response ranged from 29 to 54 months. The biochemical response ranged from 5 to 48 months. All patients with a hormonal response had objective improvement in clinical status and blood pressure. Seven patients died during the 54-month follow-up period, 4 of whom never responded to treatment. The investigators reported finding no relationship between cumulative dose and response.

Schlumberger et al.¹³ studied 11 patients with metastatic pheochromocytoma who received carrier-added iobenguane I 131 at a single institution in France between 1985 and 1990. Cumulative activity ranged from 100 to 711 mCi, in 1 to 6 courses. Moderate myelosuppression occurred in 4 patients. Symptoms improved in 55.6% (5 of 9). The tumor response proportion (95% CI) was 22.2% + 27.2% (2 of 9 evaluable patients); the tumor responses lasted 9 months and 28 months.

Loh et al.¹⁴ reviewed the literature on carrier-added iobenguane I 131 treatment for malignant pheochromocytomas and extra-adrenal paragangliomas from 1983 through 1996 in 24 centers in

10 countries. They found a total of 116 evaluable patients. A majority of the patients were selected for treatment based upon positive tracer uptake studies. The cumulative dose of carrieradded iobenguane I 131 administered ranged from 96 to 2,322 mCi, with a mean (\pm SD) of 490 + 350 mCi. The patients received a mean single therapy dose of 158 mCi and the number of doses administered ranged from 1 to 11, with a mean (\pm SD) of 3.3 + 2.2 doses. Initial symptomatic improvement was achieved in 76% of patients, tumor responses in 30%, and hormonal responses in 45%. Five patients had complete tumor and hormonal responses, ranging from 16 to 58 months, which were sustained at the time of reporting. Patients with metastases to soft tissue had more favorable responses to treatment than those with metastases to bone. No difference was noted in the age between the responders and non-responders. Adverse effects, recorded in 41% of the treated patients, were generally mild except for one fatality from bone marrow aplasia. Among 89 patients with follow-up data, 45% of the responders had relapsed with recurrent or progressive disease after a mean interval of 29.3 + 31.1 months (median 19 months). Of patients with an initial response to carrier-added iobenguane I 131, death was reported in 33% after a mean (\pm SD) of 23.2 + 8.1 months (median 22 months) following treatment. Of non-responders, death was reported in 45% after a mean (\pm SD) of 14.3 + 8.3 months (median 13 months). The reviewers concluded that carrier-added iobenguane I 131 therapy may be a useful adjunct in selected patients with malignant pheochromocytoma or paraganglioma.

Mukherjee et al.¹⁵ reported carrier-added iobenguane I 131 treatment of 15 patients with metastatic pheochromocytoma or paraganglioma. The patients were treated repeatedly to a cumulative dose of 592 mCi; this ranged from 200 to 1,592 mCi. No patients had complete remissions, but 82% had stable disease. The overall 5-year survival was 85%. Hormonal control was attained in 53%.

Safford et al.¹⁶ retrospectively report the experience of a single institution in the US in treating 22 patients with metastatic pheochromocytoma and 11 patients with paraganglioma over a 10-year period. Patients received a mean (\pm SD) administered activity of 388 \pm 131 mCi. The investigators found that patients administered > 500 mCi on their initial course of carrier-added iobenguane I 131 had improved overall survival (3.8 years versus 2.8 years, p = 0.02). By univariate analyses, the authors also found that both symptom improvement (p < 0.01) and biochemical response (p = 0.01) were associated with increased overall survival.

Rose et al.¹⁷ prospectively studied carrier-added iobenguane I 131 in 12 patients with malignant pheochromocytoma or paraganglioma at a single institution in the US. The disease was required to have been metastatic or unresectable at baseline. Patient age ranged from 10 to 58 years, with a median of 31 years. First, bone marrow/stem cells were harvested for all patients. Six patients received only 1 treatment, 5 patients received 2 treatments, and 1 patient received 3 treatments. Single treatment activity ranged from 5.6 to 18.3 mCi/kg, with a median of 11.5 mCi/kg. The activities of repeat treatments averaged within \pm 2% of prior treatments. Grade 3 thrombocytopenia occurred following 15 of the 19 treatments (78.9%). Grade 3 neutropenia occurred following 10 of the 19 treatments (52.6%) and grade 4 neutropenia occurred following 4 of the 19 treatments (21.1%). One patient needed stem cell infusion and 1 developed primary ovarian failure. There were 2 complete and 2 partial responses by RECIST criteria; the response proportion (95% CI) was 36.4% \pm 28.4% (4 of 11 evaluable patients). Duration of response ranged from 6 to 101 months, with a median of 15 months. Improvement of symptoms occurred among 90.0% \pm 18.6% (9 of 10 evaluable patients). Duration of symptom improvement ranged

from 2 to 101 months, with a median of 43 months. No dose-response effect was seen in terms of either cumulative activity or cumulative activity per kilogram.

